# **SYNOPSIS**

TITLE	Phase II Randomized, Double-Blind Study of mFOLFIRINOX plus Ramucirumab versus mFOLFIRINOX plus placebo in Advanced Pancreatic Cancer Patients		
SHORT TITLE	Phase II Randomized Trial of mFOLFIRINOX +/- Ramucirumab in Advanced Pancreatic Cancer		
PHASE	II		
OBJECTIVES	Primary Objective: Estimate and compare progression free survival (PFS) of mFOLFIRINOX plus Ramucirumab (RAM) versus mFOLFIRINOX plus placebo in subjects with recurrent or metastatic pancreas cancer (PCA) who present for first line chemotherapy treatment.		
	
 
Secondary Objectives:
 
Estimate and compare the median overall survival (mOS) in each arm.
 
Evaluate and compare the response rate (RR) in each arm.
 
Evaluate and compare the toxicities in each arm.
 
		
STUDY DESIGN	Phase II, multicenter, double-blinded, randomized, 2-arm trial evaluating efficacy and safety of mFOLFIRINOX plus ramucirumab (Arm A) vs. mFOLFIRINOX plus placebo (Arm B) in 85 subjects with advanced PCA, not amenable to curative treatment. Both arms will continue treatment until disease progression or unacceptable toxicity.		
ELIGIBILITY CRITERIA	Each of the criteria in the checklist that follows must be met in order for a subject to be considered eligible for this study.		
	
 
Inclusion Criteria
 
Written informed consent and HIPAA authorization for release of personal health information. NOTE: HIPAA authorization may be included in the informed consent or obtained separately.
 
Age ≥ 18 years at the time of consent.
 
ECOG Performance Status of 0-1 within 7 days prior to registration.
 
Histologic or cytological diagnosis of recurrent or metastatic pancreas adenocarcinoma (PCA) who present for first line chemotherapy treatment.
 
No prior first line systemic treatment (prior adjuvant or neoadjuvant treatment is permitted). Subjects whose disease has progressed after 6 months of last systemic chemotherapy or
 
		

- chemo-radiation in the adjuvant or neoadjuvant setting are eligible.
- 6. Measurable disease determined using guidelines of RECIST 1.1. Baseline tumor assessment should be performed using high resolution CT scans or MRI.
- 7. Urine protein < 1+ on dipstick test or routine urinalysis. If the proteinuria on these tests is  $\ge 2+$ , then a 24-hour urine test must be collected and must demonstrate < 1 g protein in 24 hours to allow participation
- 8. Estimated life expectancy of > 12 weeks, as assessed by the site investigator.
- 9. If sexually active, must be postmenopausal, surgically sterile, or using effective contraception (hormonal or barrier methods) due to unknown risk of teratogenicity of ramucirumab
- 10. Demonstrate adequate organ function as defined in Table 1 below; all screening labs to be obtained within 7 days prior to registration.

Table 1: Organ Function Requirements

System	Laboratory Value
Hematological	
Hemoglobin	$\geq$ 9 g/dL
Absolute Neutrophil Count (ANC)	$\geq 1,500/\text{mm}^3$
Platelet Count (PLT)	$\geq 100,000/\text{mm}^3$
Renal	
Creatinine or	$\leq 1.5 \text{ mg/dL}$
Creatinine clearance 	≥ 40 mL/min
Albumin	$\geq$ 2.5 g/dL
Hepatic	
Bilirubin	$\leq 1.5 \text{ mg/dL}$
Aspartate aminotransferase (AST)	$\leq$ 3 × ULN
	or <5 xULN in the setting
	of liver metastases
Alanine aminotransferase (ALT)	$\leq 3 \times ULN$
	or <5 xULN in the setting
	of liver metastases
Coagulation	
International Normalized Ratio (INR)	The subject has adequate
Patients receiving warfarin must be	coagulation function as
switched to low molecular weight	defined by International
heparin and have achieved stable	Normalized Ratio (INR)
coagulation profile prior to first dose	≤1.5 and a partial
of protocol therapy.	thromboplastin time (PTT)
	(PTT/aPTT) < 1.5 x
	ULN.).

<sup>1: If serum creatinine is >1.5 times the ULN, a 24-hour urine collection to calculate creatinine clearance must be performed

#### **Exclusion Criteria**

- 11. Subjects with histology other than adenocarcinoma; Examples include: neuroendocrine tumors, acinar cell cancer, sarcoma or lymphoma of the pancreas
- 12. Ongoing or active infection
- 13. Symptomatic congestive heart failure, unstable angina pectoris, symptomatic or poorly controlled cardiac arrhythmia. Symptomatic heart failure (NYHA Class II-IV)
- 14. Uncontrolled or poorly-controlled hypertension (>160 mmHg systolic or > 100 mmHg diastolic for >4 weeks) despite standard medical management.
- 15. Acute or sub-acute intestinal obstruction
- 16. Interstitial pneumonia or interstitial fibrosis of the lung, which in the opinion of the site investigator could compromise the subject or the study
- 17. Pleural effusion or ascites that causes > grade 1 dyspnea
- 18. Cirrhosis at a level of Child-Pugh B (or worse) or cirrhosis (any degree) with a history of hepatic encephalopathy or clinical meaningful ascites resulting from cirrhosis; clinically meaningful ascites is defined as ascites resulting from cirrhosis and requiring ongoing treatment with diuretics and/or paracentesis
- 19. Grade 3 or higher bleeding event  $\leq$  3 months prior to randomization.
- 20. Experience of any arterial thrombotic or arterial thromboembolic events, including, but not limited to myocardial infarction, transient ischemic attack, or cerebrovascular accident,  $\leq 6$  months prior to randomization.
- 21. History of deep vein thrombosis, pulmonary embolism, or any other significant thromboembolism (venous port or catheter thrombosis or superficial venous thrombosis are not considered "significant") during the 3 months prior to randomization.
- 22. GI perforation/fistula
- 23. Documented and/or symptomatic or known brain or leptomeningeal metastases.
- 24. Severely immune-compromised (other than being on steroids) including known HIV infection
- 25. Concurrent active malignancy, other than adequately treated non-melanoma skin cancer, other noninvasive carcinoma, or in situ neoplasm. A subject with previous history of malignancy is eligible, provided that he/she has been disease-free for > 3 years.
- 26. Breast-feeding or pregnant. Serum pregnancy test for women of child-bearing potential must be performed within 7 days prior to first dose of study treatment
- 27. Prior autologous or allogeneic organ or tissue transplantation.
- 28. Known allergy to any of the treatment components
- 29. The patient has undergone major surgery within 28 days prior to

- first dose of protocol therapy, or minor surgery/subcutaneous venous access device placement within 2 days prior to first dose of protocol therapy. The patient has elective or planned major surgery to be performed during the course of the clinical trial.
- 30. Have any condition that does not permit compliance with the study schedule including psychological, geographical, or medical.
- 31. Receiving medications that can affect clotting ability: including warfarin, aspirin (once-daily aspirin use- maximum dose 325 mg/day is permitted), nonsteroidal anti-inflammatory drugs (NSAIDs, including ibuprofen, naproxen, and others), dipyridamole or clopidogrel, or similar agents.
- 32. Serious or non-healing wound, ulcer, or bone fracture within 28 days prior to first dose of protocol therapy.

# STATISTICAL CONSIDERATIONS

We aim to test the null hypothesis of PFS at 6 months. Using a one-sided log-rank test we have estimated a sample size of 85 patients (43 in one and 42 in another arm) which will provide 80% power under a type 1 error of 20%. This is an estimation on 24 months accrual and 9 months follow up after accrual for the primary endpoint. Sample size may increase to 95 to account for a 10% drop out rate.

The primary endpoint of this clinical trial is PFS. PFS is defined as the time from enrollment to the time of progression or death. An interim analysis with Kaplan Meier method and Logrank test will be conducted after 23 subjects have been enrolled in each arm and followed up for 9 months. The trial will stop if it detects a significant difference of 3 months in PFS between the study arm-mFOLFIRINOX/RAM, as compared to the standard arm-mFOLFIRINOX at the significance level of 0.0013 according to the O'Brien-Fleming approach. Otherwise the trial will continue until the targeted sample size has been completed.

RR, PFS and OS will be reported with 95% confidence intervals. Response is defined as a complete or partial response according to CT/MRI evaluations based on RECIST 1.1 criteria. Toxicity will be graded using CTCAE v4

**Early stopping:** In the case of excessive toxicity, safety-stopping rules will be used. A grade  $\geq 3$  or adverse event that will lead to stop or termination of treatment is defined as suspected treatment related toxicity observed in the first 4 weeks of enrollment after dose modification, but excluding: nausea or vomiting and hematologic toxicities if not adequately treated. Ramucirumab will be held for drug related adverse events grade  $\geq 3$  until recovery to grade  $\leq 1$  and then resumed with a lower dose level -1 (6 mg/kg). If the grade  $\geq 3$  related adverse events does not resolve within 3 weeks of holding treatment, subject will be taken off the trial. In the case of prolonged or medically concerning grade 2 toxicity related to chemotherapy combination, treatment will be interrupted until

[figure not shown]
	recovery to grade ≤ 1, at which time treatment will be resumed at the same dose. If the adverse event does not resolve in or within 2 weeks with medical intervention, then the subject will be taken off trial.  In case of excessive toxicity, safety-stopping rules will be used. An acceptable toxicity rate will be assumed at 0.20. The study will be stopped based on an unacceptable excessive toxicity rate of 0.40. A sequential probability ratio test will be used where a likelihood ratio of 8 in favor of an excessive toxicity rate of 0.40 (vs. 0.20) provides sufficient evidence to stop the study due to excessive toxicity. Toxicity will be continuously reviewed for excessive toxicity and statistical analysis performed if excessive toxicity is suspected.  In the interim safety analysis, the study will be closed to accrual after the first 20 subjects (10 in each arm) are analyzed, if within the first cycle of treatment n/10 subjects developed any of the following grade ≥ 3 toxicity: 2/10 febrile neutropenia, 3/10 neuropathy, 3/10 hypertensive emergency or urgency, 3/10 life threatening thromboembolic event, 2/10 GI perforation or 2/10 bleeding or hemorrhage, the regimen mFOLFIRINOX RAM will be considered toxic and the trial will stop.
TOTAL NUMBER OF SUBJECTS	N = 85 to 95
ESTIMATED ENROLLMENT PERIOD	Estimated 24 months
ESTIMATED STUDY DURATION	Estimated 33 months

Page 8 of 51

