# 6.1 Dose Modifications for Ramucirumab/placebo

Ramucirumab/placebo will be held for Grade  $\geq 3$  study drug related adverse events until recovery to Grade  $\leq 1$  and then resume with a dose reduction (level -1; 6 mg/kg) if site investigator evaluation relates toxicity to ramucirumab/placebo. If a second Grade  $\geq 3$  drug related adverse event is experienced and does not resolve within 2 weeks of the initial dose reduction, an additional dose reduction (level -2; 5mg/kg) will be made. If Grade  $\geq 3$  related adverse event does not resolve within 2 weeks of the second dose reduction, the subject will be taken off the trial.

Table 3. Modified dose of ramucirumab

Dose level	Ramucirumab
Starting dose	8 mg/kg
Level -1 dose reduction	6 mg/kg
Level -2 dose reduction	5 mg/kg

Version Date: 13AUG2018 Confidential Page 20 of 51

Table 4. Dosing level of ramucirumab/placebo for treatment related adverse events

Toxicity NCI	Worst Interval Toxicity	Day of Treatment
Grade (value)		
1	Maintain dose level	Continue treatment per protocol schedule.
2	Maintain dose level	Hold until resolved to grade 1 or less.
3	Reduce to dose level -1 6 mg/kg	Hold until resolved to grade 1 or less.
4	Reduce to dose level -2 5 mg/kg	Hold until resolved to grade 1 or less.

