#### **6.1.1** Management of Hypertension

Interrupt ramucirumab/placebo for severe hypertension until controlled with medical management. Permanently discontinue ramucirumab/placebo for severe hypertension that cannot be controlled with antihypertensive therapy. The subject will continue to be followed per guidelines in Section 7. Subjects with grade 4 hypertension must not receive further treatment with ramucirumab

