## 11.6 Excessive Toxicity – Criteria for Stopping and Interim Safety Analysis

In case of excessive toxicity, safety-stopping rules will be used. An acceptable toxicity rate will be assumed at 0.20. The study will be stopped based on an unacceptable excessive toxicity rate of 0.40. A sequential probability ratio test will be used where a likelihood ratio of 8 in favor of an excessive toxicity rate of 0.40 (vs. 0.20) provides sufficient evidence to stop the study due to excessive toxicity. Data will be continuously reviewed for excessive toxicity and statistical analysis performed if excessive toxicity is suspected. The table below provides the minimum number of patients exhibiting excessive toxicity that will trigger statistical analysis.

Total number of treated patients	Number of Patients observed with excessive toxicity
3	≥2
4-5	≥3
6-7	≥4
8-9	≥5
10-11	≥6
12-13	≥7
14-16	≥8
17-18	≥9
19-20	≥10

Version Date: 13AUG2018 Confidential Page 41 of 51

21-23	≥11
24-25	≥12
26-28	≥13
29-30	≥14
31-33	≥15
34-35	≥16
36-38	≥17
39-40	≥18

Ramucirumab will be held for drug related adverse events Grade  $\geq 3$  until recovery to Grade  $\leq 1$  and then resumed with a lower dose level -1 (6 mg/kg). If the Grade  $\geq 3$  related adverse event does not resolve within 4 weeks of holding treatment, the subject will be taken off study treatment.

In the case of prolonged or medically concerning Grade 2 toxicity related to the chemotherapy combination, treatment will be interrupted until recovery to Grade  $\leq 1$ , at which time treatment will be resumed at the same dose. If the adverse event does not resolve in or within 2 weeks with medical intervention, then the subject will be taken off study treatment.

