## 11.6.1 Excessive Toxicity

Excessive toxicity is defined as any adverse event that meets the following criteria:

- Any grade 3 or higher adverse event or an adverse event that leads to discontinuation of study therapy.
- The adverse event must be possibly, probably or definitely related to any of the study treatments (Ramucirumab, Oxaliplatin, Irinotecan, 5-FU)
- The adverse event occurs in the first four weeks of treatment
- The adverse event grade does not diminish to grade 1, four weeks after dose modification or dose delay. AE must have been adequately treated (e.g. nausea, vomiting, hematologic toxicities)

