## 11.6.2 Interim Safety Analysis

The study will be closed to accrual and an interim safety analysis conducted after ten subjects are accrued to each arm. If the following rates of selected toxicities listed below are observed within the first cycle of treatment (four weeks), the regimen (Ramucirumab, Oxaliplatin, Irinotecan, 5-FU) will be considered toxic and the trial will be stopped.

Adverse Event (≥ grade 3)	Toxicity Rate (n/10 subjects)
Febrile Neutropenia	2/10
Peripheral Motor or Sensory Neuropathy	3/10
Hypertension	3/10
Life Threatening Thromboembolic Event	3/10
GI Perforation	2/10
Hemorrhage, Bleeding	2/10

Version Date: 13AUG2018 Confidential Page 42 of 51

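### The ten-per-arm safety stopping rule defines its hypertension criterion in two ways, so the same ten patients could stop the trial under one text and not under the other

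*Combined protocol and SAP*

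**What the plan says.** **Stopping rule.** In the synopsis (Statistical Considerations, early stopping), the trial stops if, within the first cycle, the patients reviewed show "any of the following grade ≥ 3 toxicity: 2/10 febrile neutropenia, 3/10 neuropathy, 3/10 hypertensive emergency or urgency", or reach one of three further thresholds. Section 11.6.2 gives the rule as a table, introduced by "If the following rates of selected toxicities listed below are observed within the first cycle of treatment (four weeks". Its event column is headed "Adverse Event (≥ grade 3", and the hypertension row carries 3/10 with no further condition. The n/10 thresholds agree on all six rows. Only the hypertension row has a materially different event definition.

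**Management of hypertension.** Section 6.1.1 tells sites: "Interrupt ramucirumab/placebo for severe hypertension until controlled with medical management". It requires permanent discontinuation if severe hypertension cannot be controlled, or if it is Grade 4.

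**Hold limit.** For a related Grade 3 or higher event during a ramucirumab hold, the synopsis says that if it "does not resolve within 3 weeks of holding treatment, subject will be taken off the trial". Section 11.6 says that if it "does not resolve within 4 weeks of holding treatment, the subject will be taken off study treatment". Section 6.1 has a third limit, 2 weeks counted from the second dose reduction.

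**Dose after Grade 4.** For any Grade 3 or higher event, the text of 6.1 directs sites to hold and "then resume with a dose reduction (level -1; 6 mg/kg) if site investigator evaluation relates toxicity to ramucirumab/placebo". The synopsis and 11.6 also resume at 6 mg/kg. Table 4, in the same section 6.1, sends Grade 4 to level -2, 5 mg/kg.

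**The concern.** A stopping rule should give one answer for one set of data. Here the synopsis applies two conditions together (grade, and emergency or urgency), while 11.6.2 applies only the grade. The synopsis events are therefore a subset of the 11.6.2 events, and the synopsis rule can never stop the trial more readily. A patient with Grade 3 hypertension that is neither an emergency nor an urgency counts under one text only.

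This row decides whether the trial continues. If three such patients appeared among ten on ramucirumab, someone would have to choose the criterion after seeing the data. Hypertension is among the reported ramucirumab events in section 9.1.5, so the row is not idle.

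The other two differences act on individual patients. Between day 21 and day 28 of a hold, one text removes the patient and the other does not. After some Grade 4 events, sites have two resumption doses.

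**Working it through.** The 3/10 threshold is set by rule, with no derivation, so there is no plan figure to reproduce. The arithmetic only bounds how far the two criteria can diverge.

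**Inputs from the protocol:** 10 patients per arm; threshold 3 of 10; febrile neutropenia threshold 2 of 10; ramucirumab levels 8, 6 and 5 mg/kg; interruption limit of 30 days or more (6.3 and 7.1.4).

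**Assumed, because the protocol gives no first-cycle rates:** q, the true rate of Grade 3 or higher hypertension in the ramucirumab arm; f, the share of those events that are emergencies or urgencies.

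**Formulas.** With X binomial on 10 patients:

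- Stop under 11.6.2: A = P(X ≥ 3 | q) = 1 − Σ(k = 0 to 2) C(10,k) q^k (1−q)^(10−k)
- Stop under the synopsis: B = P(X ≥ 3 | q·f)
- Because one event set lies inside the other, P(texts disagree) = A − B

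Example at q = 0.15 and f = 0.5: A = 1 − (0.1969 + 0.3474 + 0.2759) = 0.1798. B = P(X ≥ 3 | 0.075) = 0.0339. A − B = 0.1459.

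**Probability that the texts disagree on this row:**

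| Share f | q = 5% | q = 10% | q = 15% | q = 20% |
|---|---|---|---|---|
| 0 (equals A) | 0.0115 | 0.0702 | 0.1798 | 0.3222 |
| 0.25 | 0.0113 | 0.0685 | 0.1746 | 0.3107 |
| 0.50 | 0.0099 | 0.0587 | 0.1459 | 0.2520 |
| 0.75 | 0.0063 | 0.0363 | 0.0865 | 0.1424 |
| 1 | 0 | 0 | 0 | 0 |

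**From row to trial.** The decision changes only if no other row has already stopped the trial. At assumed febrile neutropenia rates of 5%, 10% and 20%, P(≥ 2 of 10) = 0.0861, 0.2639 and 0.6242. Assuming independence, at q = 0.15 and f = 0.5:

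- 0.1459 × (1 − 0.0861) = 0.1333
- 0.1459 × (1 − 0.2639) = 0.1074
- 0.1459 × (1 − 0.6242) = 0.0548

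The other four rows would lower these further.

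**Hold limit.** 3 weeks = 21 days and 4 weeks = 28 days. Both are below 30 days, so the interruption rule does not favour either. The section 6.1 limit runs from a dose reduction, not from the start of a hold, and neither of the other two texts is reconciled with it.

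**Grade 4 dose.** 1 − 6/8 = 25% below the starting dose; 1 − 5/8 = 37.5% below it. Sections 6.1.1 and 6.1.6 already require permanent discontinuation for several Grade 4 events, including hypertension, bleeding and infusion reactions. What remains is, for example, Grade 4 neutropenia that the investigator attributes to ramucirumab: neutropenia is listed in 9.1.5 and absent from 6.1.6.

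**The case against.** **The practical gap may be small.** The protocol defines neither hypertensive urgency nor Grade 3 hypertension; it only points to CTCAE v4. Section 6.1.1 speaks of severe hypertension, names a grade only for Grade 4, and does not place severe cases outside urgency. If urgency is read broadly, the criteria nearly coincide: at q = 15% and a 90% share, the texts disagree with probability 3.7%, and at 100% never. This stands. The conflict of wording is certain; its frequency is not.

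**The body should override the synopsis.** The protocol does not say so, and the synopsis states the rule in full operative form. Nor could this settle the Grade 4 dose, where text and table conflict inside section 6.1.

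**The synopsis may be what was meant.** It fits the management rule in 6.1.1, and the thromboembolic row is limited to life-threatening events in both texts. This is a fair reading, so the sponsor must be free to choose it.

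**Four weeks might seem to be the intended hold limit.** A reader might infer this from the 30-day interruption rule and from the phrase "four weeks after dose modification or dose delay" in 11.6.1. Neither supports it. The 30-day rule accommodates 21 days equally well, and 11.6.1 defines an excessive-toxicity event for the sequential test; it does not set a limit on holding ramucirumab.

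**Table 4 can be read as the specific rule for Grade 4.** That is reasonable, and with the 6.1.6 exclusions it makes this part minor. The mismatch remains, because the text of 6.1 uses level -2 as the second reduction.

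**Conclusion.** The point holds as a contradiction in a trial-level decision rule. Three of ten ramucirumab patients with Grade 3 hypertension and no emergency or urgency stop the trial under 11.6.2 and do not, on this row, under the synopsis.

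Its frequency cannot be stated. The disagreement runs from zero to 1.2%, 7.0%, 18.0% or 32.2% at assumed Grade 3 or higher rates of 5%, 10%, 15% or 20%. It is smaller at trial level, where other rows may stop the trial anyway. A reader might take the middle of the table as an expected rate; the protocol supplies neither the rate nor the emergency share, so these are bounds only.

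The hold limit is a real but secondary conflict, with three time limits to reconcile. The Grade 4 dose is minor.

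A reader might also infer damage to the efficacy analysis, for instance because some texts speak of removal from the trial. The documents do not support that: 6.3 and 7.1.6 keep patients who stop treatment in follow-up. The primary test, the sample size and the sequential toxicity table are unaffected.

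**What to change.** 1. **Hypertension row.** Before the ten-per-arm data are reviewed, use one criterion in both places. The default is to change the synopsis item to 3/10 with hypertension of Grade 3 or higher, as in 11.6.2, because that wording is more protective and sits in the statistical section. If the sponsor intends emergencies or urgencies only, amend the 11.6.2 row instead.
2. **Hold limit.** The sponsor should choose 3 or 4 weeks, use it in the synopsis and 11.6, and state how it works with the 6.1 limit of 2 weeks after the second dose reduction.
3. **Grade 4 dose (minor).** For events not requiring permanent discontinuation, the sponsor should choose level -1 or level -2 and apply it in the text of 6.1, Table 4, the synopsis and 11.6. If level -2 is kept, state what follows a further Grade 3 or higher event, since no lower level exists.

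**Cost.** These are wording changes that need no new data and leave the sample size alone. Under section 13.5 an amendment needs approval by the sponsor-investigator, the drug supplier and each site's IRB. The default in item 1 also makes stopping on this row more frequent than the synopsis wording would: 18.0% against 3.4% at an assumed 15% rate with half the events emergencies or urgencies. That includes stopping for hypertension that 6.1.1 allows to be managed.
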